5.8.1 Discontinuation of Study Therapy after CR

Among patients who are not at the conclusion of 4 cycles of pembrolizumab candidates for surgery, or for those who refuse surgery at that time point, pembrolizumab will be continued for one year. Discontinuation of pembrolizumab in this cohort may be considered for subjects who subsequently attain a confirmed CR and have been treated for at least 24 weeks with pembrolizumab and had at least two treatments with pembrolizumab beyond the date when the initial CR was declared.

5.9 Subject Replacement Strategy

Patients will be replaced if they do not receive at least one cycle of pembrolizumab.

5.10 Clinical Criteria for Early Trial Termination

Early trial termination will be the result of the criteria specified below:

1. Quality or quantity of data recording is inaccurate or incomplete
2. Poor adherence to protocol and regulatory requirements
3. Incidence or severity of adverse drug reaction in this or other studies indicates a potential health hazard to subjects
4. Plans to modify or discontinue the development of the study drug
5. An early stopping rule will be put into place such that if at any time during enrollment of the first 10 patients considered initially resectable at screening, if 3 or more of these patients have local progression on the study treatment and are then deemed locally unresectable the trial will close early.

In the event of Merck decision to no longer supply study drug, ample notification will be provided so that appropriate adjustments to subject treatment can be made.

6.0 TRIAL FLOW CHART

6.1 Study Flow Chart

Trial Period:	Screening Phase	Study Treatment Cycles					Continuation Treatment Cycles				End of Treatment		Post-Treatment	
		Main Study Screening (Visit 1)	1	2	3	4	4D21	To be repeated beyond 8 cycles				Discon	Safety Follow-up	Follow Up Visits
Scheduling Window (Days):	-28 to -1		± 3	± 3	± 3	± 7	± 7	5	6	7	8			
Administrative Procedures														
Informed Consent	X													
Inclusion/Exclusion Criteria	X													
Demographics and Medical History	X													
Prior and Concomitant Medication Review	X	X	X	X	X		X	X	X	X	X			
Pembrolizumab Administration		X	X	X	X		X	X	X	X				
Post-study anticancer therapy status													X	X
Survival Status														X
ENT evaluation for resectability status	X					X ¹⁴					X ¹⁴			
Clinical Procedures/Assessments														
Review Adverse Events		X	X	X	X		X	X	X	X	X	X ¹	X ¹³	X ¹³
Full Physical Examination	X													
Directed Physical Examination		X	X	X	X		X	X	X	X	X			X
Vital Signs and Weight ²	X	X ³	X ³	X ³	X ³		X ³	X ³	X ³	X ³	X			X
ECOG Performance Status	X	X ⁴	X ⁴	X ⁴	X ⁴		X ⁴	X ⁴	X ⁴	X ⁴	X			X
Laboratory Procedures/Assessments: analysis performed by LOCAL laboratory														
Pregnancy Test – Urine or Serum β-HCG	X													
PT/INR and aPTT	X ⁵													
CBC with Differential	X ⁵	X	X ⁶	X ⁶	X ⁶		X ⁶	X ⁶	X ⁶	X ⁶	X			
Comprehensive Serum Chemistry Panel, Magnesium, Phosphorous, LDH, LFTs	X ⁵	X	X ⁶	X ⁶	X ⁶		X ⁶	X ⁶	X ⁶	X ⁶	X			
Urinalysis	X ⁵		X ⁶		X ⁶			X ⁶		X ⁶				
T3, FT4 and TSH	X ⁵		X ⁶		X ⁶			X ⁶		X ⁶				

Trial Period:	Screening Phase	Study Treatment Cycles					Continuation Treatment Cycles				End of Treatment		Post-Treatment			
		Treatment Cycle/Title:	Main Study Screening (Visit 1)	1	2	3	4	4D21	5	6	7	8	Discon	Safety Follow-up	Follow Up Visits	Survival Follow-Up
Scheduling Window (Days):				-28 to -1	± 3	± 3	± 3	± 7	± 3	± 3	± 3	± 3	At time of Discon ± 3	30 days post discon ¹ ± 7	Every 8 weeks post discon ± 7	Every 12 weeks ± 7
Efficacy Measurement																
CT neck/chest/abdomen/pelvis	X ⁷		X ¹¹		X ¹¹			X ¹¹		X ¹¹		X ¹²				
Tumor Biopsies/Archival Tissue Collection/Correlative Studies Blood																
Archival Tissue Collection	X ⁸															
Newly Obtained Tissue Collection	X ⁹					X ¹⁰					X ¹⁰					
Correlative Studies Blood Collection	X					X					X ¹⁵					

1. In the case that a patient initiates a subsequent anti-cancer therapy the 30 day follow up should occur prior to the first dose of the new therapy and patients will move to survival follow up.
2. Vital signs should include temperature, pulse, respiratory rate, weight and blood pressure. Height will be measured at screening only.
3. Vital signs will be taken prior to the administration of each dose of trial treatment and at discontinuation of each treatment.
4. ECOG status will be evaluated prior to the administration of each dose of trial treatment and at discontinuation of each treatment.
5. Screening lab will be assessed within 14 days of first treatment.
6. After cycle 1, pre-treatment labs can be drawn up to 72 hours pre-dose.
7. The baseline CT scan can be from before study enrollment as long as the scan is within 4 weeks of study treatment.
8. Archival tissue from a biopsy prior to radiation treatment with or without systemic therapy should be requested.
9. All patients will have a biopsy prior to the start of study treatment. This specimen may be obtained up to 6 weeks (42 days) prior to initiation of treatment on Day 1 and following completion of RT/CRT. This pre-treatment biopsy can be used to confirm residual disease.
10. Patients will have a research biopsy after completion of the 4th treatment cycle or at study discontinuation if they come off treatment before cycle 4. There will be no additional biopsy for patients who stay on treatment past 4 cycles.
11. Imaging during study treatment cycles will occur at the end of cycle 2 when clinically indicated and cycle 4 or at disease progression whichever comes first (required). Less frequent imaging is acceptable during the continuation cycles, although a minimum of every 8 weeks is recommended.
12. If a patient comes off trial for reasons other than disease progression imaging should be done every 9 weeks ±7 days
13. Information on SAEs will be collected for 90 days after the end of treatment. Any unexpected SAE that occurs more than 90 days after drug administration but is possibly, probably or definitely attributed to drug administration will be recorded and reported.
14. Patients will have a repeat ENT evaluation for resectability status after completion of the 4th treatment cycle or at study discontinuation if they come off treatment before cycle 4. There will be no additional ENT evaluation for patients who stay on treatment past 4 cycles
15. Correlative blood collection will occur at end of cycle 4 as well as at discontinuation, unless discontinuation within past 21 days.

6.2 Trial Procedures

The Trial Flow Chart - Section 6.0 summarizes the trial procedures to be performed at each visit. Individual trial procedures are described in detail below. It may be necessary to perform these procedures at unscheduled time points if deemed clinically necessary by the investigator.

Furthermore, additional evaluations/testing may be deemed necessary by the Sponsor and/or Merck for reasons related to subject safety. In some cases, such evaluation/testing may be potentially sensitive in nature (e.g., HIV, Hepatitis C, etc.), and thus local regulations may require that additional informed consent be obtained from the subject. In these cases, such evaluations/testing will be performed in accordance with those regulations.

6.2.1 Patient Registration Process

Prior to obtaining signed consent from a patient, the site principal investigator or coordinator must email the project manager to inquire about study space availability. If a slot is available, the Project Manager will provide a study ID and the potential study participant will complete the consent process. The informed consent process must be completed before any study screening procedures may begin. Following consent, patients will have all required screening procedures outlined in Section 6. The site principal investigator or other approved investigator must document that the patient has met all inclusion criteria and has none of the exclusion criteria. Following completion of eligibility testing, eligibility documents will be sent to the project manager. Examples of required documents are listed in the manual of operations.

Upon review and approval of the Project Manager an email will be sent to the site with confirmation of eligibility.

6.2.2 Administrative Procedures

6.2.2.1 Informed Consent

The Investigator must obtain documented consent from each potential subject prior to participating in a clinical trial.

6.2.2.2 General Informed Consent

Consent must be documented by the subject's dated signature or by the subject's legally acceptable representative's dated signature on a consent form along with the dated signature of the person conducting the consent discussion.

A copy of the signed and dated consent form should be given to the subject before participation in the trial. The consent process must be documented and available for review in the patients research chart.

The initial informed consent form, any subsequent revised written informed consent form and any written information provided to the subject must receive the IRB/ERC's approval/favorable opinion in advance of use. The subject or his/her legally acceptable

representative should be informed in a timely manner if new information becomes available that may be relevant to the subject's willingness to continue participation in the trial. This can occur via written documentation (a formal letter), in person conversation or a phone call prior to an amended consent document becoming available. Regardless of the method the procedure must be documented and kept in the research file. As soon as possible this information will be provided and documented via a revised consent form or addendum to the original consent form that captures the subject's dated signature or by the subject's legally acceptable representative's dated signature.

Specifics about a trial and the trial population will be added to the consent form template at the protocol level and will be provided to sites by the sponsor.

The informed consent will adhere to IRB/ERC requirements, applicable laws and regulations and Sponsor requirements.

6.2.2.3 Inclusion/Exclusion Criteria

All inclusion and exclusion criteria will be reviewed by the local investigator. All patients will be registered to this trial locally by the project manager. See Patient Registration (section 6.2.1) for more information.

6.2.2.4 Medical History

A medical history will be obtained by the investigator or qualified designee. Medical history will include all active conditions, and any condition diagnosed within the prior 10 years that are considered to be clinically significant by the Investigator. Details regarding the disease for which the subject has enrolled in this study will be recorded separately and not listed as medical history.

6.2.2.5 Prior and Concomitant Medications Review

6.2.2.5.1 Prior Medications

The investigator or qualified designee will review prior medication use, including any protocol-specified washout requirement, and record prior medication taken by the subject within 28 days before starting the trial. Treatment for the disease for which the subject has enrolled in this study will be recorded separately and not listed as a prior medication.

6.2.2.5.2 Concomitant Medications

The investigator or qualified designee will record medication, if any, taken by the subject during the trial. All medications related to reportable SAEs and ECIs should be recorded as defined in Section 6.3.

6.2.2.6 Disease Details and Treatments

6.2.2.6.1 Disease Details

The investigator or qualified designee will obtain prior and current details regarding disease status.

6.2.2.6.2 Prior Treatment Details

The investigator or qualified designee will review all prior cancer treatments including systemic treatments, radiation and surgeries.

6.2.2.6.3 Subsequent Anti-Cancer Therapy Status

The investigator or qualified designee will review all new anti-neoplastic therapy initiated after the last dose of trial treatment. If a subject initiates a new anti-cancer therapy within 30 days after the last dose of trial treatment, the 30 day Safety Follow-up visit must occur before the first dose of the new therapy. Once new anti-cancer therapy has been initiated the subject will move into survival follow-up.

6.2.2.7 Adverse Event (AE) Monitoring

The investigator or qualified designee will assess each subject to evaluate for potential new or worsening AEs as specified in the Trial Flow Chart and more frequently if clinically indicated. Adverse experiences will be graded and recorded throughout the study and during the follow-up period according to NCI CTCAE Version 4.0 (see Section 10.2). Toxicities will be characterized in terms regarding seriousness, causality, toxicity grading, and action taken with regard to trial treatment.

For subjects receiving treatment with pembrolizumab all AEs of unknown etiology associated with pembrolizumab exposure should be evaluated to determine if it is possibly an event of clinical interest (ECI) of a potentially immunologic etiology (termed immune-related adverse events, or irAEs).

Please refer to section 6.3 for detailed information regarding the assessment and recording of AEs.

6.2.2.8 Full Physical Exam

The investigator or qualified designee will perform a complete physical exam during the screening period. Clinically significant abnormal findings should be recorded as medical history. A full physical exam should be performed during screening,

6.2.2.9 Directed Physical Exam

For cycles that do not require a full physical exam per the Trial Flow Chart, the investigator or qualified designee will perform a directed physical exam as clinically indicated prior to trial treatment administration.

6.2.2.10 Vital Signs

The investigator or qualified designee will take vital signs at screening, prior to the administration of each dose of trial treatment and at treatment discontinuation as specified in the Trial Flow Chart (Section 6.0). Vital signs should include temperature, pulse, respiratory rate, weight and blood pressure. Height will be measured at screening only.

6.2.2.11 Eastern Cooperative Oncology Group (ECOG) Performance Scale

The investigator or qualified designee will assess ECOG status (see Section 10.1) at screening, prior to the administration of each dose of trial treatment and discontinuation of trial treatment as specified in the Trial Flow Chart.

6.2.2.12 Tumor Imaging and Assessment of Disease

CT neck, chest, abdomen and pelvis will be ordered at baseline and during the 3rd week of cycles 2, if clinically indicated, cycle 4 or at time of progression whichever comes first. Additional re-imaging may be obtained at the discretion of the investigator. For patients who are not amenable to resection following 4 cycles of therapy and who continue on pembrolizumab, a q8 week CT of the neck, chest, abdomen and pelvis will be obtained.

6.2.2.12.1 Measurement of Response

Following pembrolizumab, response will be measured in comparison to the most immediate pre-pembrolizumab imaging study. For complete definitions of measurable and non-measurable disease, please refer to the RECIST v1.1 criteria.

1. For lesions that meet the criteria for measurable disease outlined in RECIST 1.1, the standard RECIST response criteria will apply

RECIST response criteria:

Complete response: Disappearance of all target lesions. Any pathological lymph nodes (whether target or non-target) must have reduction in short axis to <10 mm.

Partial response: At least a 30% decrease in the sum of diameters of target lesions, taking as reference the baseline sum diameters.

Progressive disease: At least a 20% increase in the sum of diameters of target lesions, taking as reference the smallest sum on study (this includes the baseline sum if that is the smallest on study). In addition to the relative increase of 20%, the sum must also

demonstrate an absolute increase of at least 5 mm. (Note: the appearance of one or more new lesions is also considered progression).

Stable disease: Neither sufficient shrinkage to qualify for PR nor sufficient increase to qualify for PD, taking as reference the smallest sum diameters while on study.

2. The following 2 criteria for evaluation of clinical response will apply for **lesions considered too small for measurement by RECIST 1.1** (for example nodes with short axis < 1.5cm or primary lesions or skin lesions < 1cm).

The lesion would have to shrink to < 1cm in all three dimensions and also have at least a 30% decrease in the sum of diameters of target lesions, taking as reference the baseline sum diameters.

AND

One of the following two criteria are true:

- 1) Either the biopsy performed after pembrolizumab shows no active cancer

OR

- 2) The patient has a PET scan after pembrolizumab which demonstrates that a previously active lesion (SUV \geq 3.0) is now PET negative (SUV < 3.0).

In the case where both PET and biopsy are both performed, and the results are disparate, the biopsy results will take precedence. For example a positive biopsy in this situation would connote a designation of response as a PR, and a negative biopsy would connote a response as a CR.

Response will be evaluated by imaging studies as described in the study calendar. If symptoms develop or clinical deterioration occurs, patients may be imaged prior to the pre-specified time points for imaging.

6.2.2.12.2 Evaluation of Best Overall Response

The Best Overall Response is the best response recorded from the start of the treatment until completion of four cycles of study drug (taking as reference for progressive disease the smallest measurements recorded since the treatment started). For purpose of the primary endpoint of the study, the overall response will be measured during the post pembrolizumab, in comparison to the most immediate pre-pembrolizumab imaging.

6.2.2.12.3 Progression-Free and Overall Survival

For the purpose of the secondary endpoints of this study, PFS is defined as the time from initiation of study drug until the first documented, confirmed progression of disease. PFS will

also be measured and reported from the initiation of study drug. OS will be measured from the initiation of study therapy.

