3.2 Secondary Objective(s) & Hypothesis(es)

1. To determine changes in PD-L1 expression following irradiation
 - a. Hypothesis- irradiation will increase inflammation and PD-L1 expression
2. To determine the overall response rate as a function of PD-L1 expression
 - a. Hypothesis- higher rates of PD-L1 expression will be associated with higher overall response rates
3. To evaluate median progression free survival and overall survival
 - a. Hypothesis- based on limited data from previous studies the expected rate of DFS and OS are approximately 30% and 50% respectively
4. To determine the rate of immune related adverse events in patients receiving immunotherapy following radiation with or without systemic therapy
 - a. Hypothesis- The rate of immune related events post radiation will be similar to that of the baseline rate receiving immunotherapy in the metastatic setting
5. To determine the rate of distant metastases
 - a. Hypothesis- based on limited data from previous studies the expected rate of distant metastases is approximately 33%

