5.8 Subject Withdrawal/Discontinuation Criteria

Subjects may withdraw consent at any time for any reason or be dropped from the trial at the discretion of the investigator should any untoward effect occur. In addition, a subject may be withdrawn by the investigator or the Sponsor if enrollment into the trial is inappropriate, the trial plan is violated, or for administrative and/or other safety reasons. Specific details regarding discontinuation or withdrawal are provided in Section 6– Other Procedures.

A subject must be discontinued from the trial treatment for any of the following reasons:

- The subject or legal representative (such as a parent or legal guardian) withdraws consent.
- Confirmed radiographic disease progression
- Unacceptable adverse experiences as described in Section 5.2.1.2
- Intercurrent illness that prevents further administration of treatment
- Investigator's decision to withdraw the subject
- The subject has a confirmed positive serum pregnancy test
- Noncompliance with trial treatment or procedure requirements
- The subject is lost to follow-up
- Completed 12 months of uninterrupted treatment with pembrolizumab or 17 administrations of study medication, whichever is later.
- *Note: 12 months of study medication is calculated from the date of first dose.*
Administrative reasons

The End of Treatment and Follow-up visit procedures are listed in Section 6 (Protocol Flow Chart) and Section .6.2.5 (Visit Requirements).

From the administration of first treatment until 30 days (unless otherwise specified) subsequent to last treatment or withdrawal of subject, new onset adverse events will be captured. Follow-up and reporting of these events will follow the same procedure as for AEs observed during the study period. Serious Adverse Events will be collected for 90 days after the end of treatment as described in Section 6.3. In addition, any unexpected SAE that occurs more than 90 days after drug administration but is possibly, probably or definitely attributed to drug administration will be recorded and reported.

Subjects who discontinue for reasons other than progressive disease will have post-treatment follow-up for disease status until disease progression, initiating a non-study cancer treatment, withdrawing consent or becoming lost to follow-up. After documented disease progression each subject will be followed by telephone for overall survival until death, withdrawal of consent, or the end of the study, whichever occurs first.

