6.2.5.3.2 Follow-up Visits

At each follow up visit patients will have a directed physical exam, including ECOG performance status, vital signs and weight. A comment will also be made regarding the post-study anticancer status. Subjects who discontinue trial treatment for a reason other than disease progression will move into the Follow-Up Phase and should be assessed every 8 weeks (± 7 days) with imaging done every 9 weeks (± 7 days). Every effort should be made to collect information regarding disease status until the start of new anti-neoplastic therapy, disease progression, death, or end of the study. Information regarding post-study anti-neoplastic treatment will be collected if new treatment is initiated.

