6.2.5.3.3 Survival Follow-up

Once a subject experiences confirmed disease progression or starts a new anti-cancer therapy, the subject moves into the survival follow-up phase and should be contacted by telephone

every 12 weeks to assess for survival status until death, withdrawal of consent, or the end of the study, whichever occurs first.

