The primary endpoint of this trial will be overall response rate and the secondary endpoint will be progression-free survival. We will use descriptive statistics to calculate frequency and proportion for the response rate to pembrolizumab. 95% confidence interval will also be provided. Exact binomial test will be used to compare the observed response rate versus historical control. For the secondary endpoint, we will use Kaplan-Meier estimator to present the progression-free survival.

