10.2 Common Terminology Criteria for Adverse Events V4.0 (CTCAE)

The descriptions and grading scales found in the revised NCI Common Terminology Criteria for Adverse Events (CTCAE) version 4.0 will be utilized for adverse event reporting. (<http://ctep.cancer.gov/reporting/ctc.html>)

10.3 Response Evaluation Criteria in Solid Tumors (RECIST) 1.1 Criteria for Evaluating Response in Solid Tumors

RECIST version 1.1* will be used in this study for assessment of tumor response. While either CT or MRI may be utilized, as per RECIST 1.1, CT is the preferred imaging technique in this study.

* As published in the European Journal of Cancer:

E.A. Eisenhauer, P. Therasse, J. Bogaerts, L.H. Schwartz, D. Sargent, R. Ford, J. Dancey, S. Arbuck, S. Gwyther, M. Mooney, L. Rubinstein, L. Shankar, L. Dodd, R. Kaplan, D. Lacombe, J. Verweij. New response evaluation criteria in solid tumors: Revised RECIST guideline (version 1.1). Eur J Cancer. 2009 Jan;45(2):228-47.

In addition, volumetric analysis will be explored by central review for response assessment.

11.0 REFERENCES:

6. Induction chemotherapy plus radiation compared with surgery plus radiation in patients with advanced laryngeal cancer. The Department of Veterans Affairs Laryngeal Cancer Study Group. *N Engl J Med.* Jun 13 1991;324(24):1685-1690.

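### PFS is defined without death as an event, so the planned Kaplan-Meier curve is time to progression labelled as PFS

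*Combined protocol and SAP*

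**What the plan says.** - Section 6.2.2.12.3: "PFS is defined as the time from initiation of study drug until the first documented, confirmed progression of disease". The next sentence only repeats the starting point. OS is given a starting point and no event.
- Section 3.2 lists as a secondary objective: "To evaluate median progression free survival and overall survival".
- Section 7.1 names PFS as the secondary endpoint and gives one line of method: "we will use Kaplan-Meier estimator to present the progression-free survival". It lists no events and no censoring rule.
- Section 5.8, for patients who stop treatment for reasons other than progression, plans "follow-up for disease status until disease progression, initiating a non-study cancer treatment, withdrawing consent or becoming lost to follow-up". Death is not in that list.
- Section 6.2.5.3.2 asks sites to collect "disease status until the start of new anti-neoplastic therapy, disease progression, death, or end of the study". Here death marks the end of data collection; it is not made an endpoint event.
- Section 6.2.5.3.3 has telephone contact "every 12 weeks to assess for survival status until death, withdrawal of consent, or the end of the study".
- Section 6.2.2.12.1 defines progression ("Progressive disease: At least a 20% increase in the sum of diameters of target lesions", with an absolute-increase condition and a new-lesion note) and includes no confirmation step. Section 10.3 says RECIST 1.1 "will be used in this study for assessment of tumor response".

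**The concern.** A patient who dies without documented progression has not survived progression-free, yet under the written definition that patient never has an event. The estimand is therefore time to progression. The requirement that progression be confirmed widens the gap: nothing says what confirms it, so a patient who dies after one progressing scan could also be left without an event.

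Such deaths are possible under this schedule. The flow chart footnotes (6.1), 6.2.2.12 and 6.2.5.2 make the cycle 2 scan conditional on clinical indication, so on that reading the first required scan comes after cycle 4, at about 12 weeks, unless progression comes first. (Sections 2.1 and 5.3 also describe a cycle 2 scan as performed; these passages need to be reconciled.)

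What is at stake is the interpretation of the reported median. PFS is the only secondary endpoint with a named analysis, and a single-arm PFS figure is likely to be read beside PFS figures from other studies.

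**Working it through.** **1. The plan's own design figure.** PFS has no stated sample size, event count or power. The only power figure concerns response rate (7.1): 24 patients, 10% against 27%, exact one-sided test at 0.10. The smallest rejection count with type I error at or below 0.10 is 5 of 24, with exact alpha 0.085 and power 0.817. This agrees with the stated 81% and does not involve PFS.

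**2. Text check.** Sections 3.2, 5.8, 6.2.2.12.3, 6.2.5.3.2, 6.2.5.3.3 and 7.1 were set side by side. One names an endpoint event (progression). None makes death an event, and none says how a patient who dies without progression is handled.

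**3. Effect on the curve, deaths censored on the day of death.** Assumptions: 24 patients, 17 ordered first events, no other censoring, *k* of the 17 being deaths without progression, all orderings weighted equally. Neither 17 nor *k* comes from the documents. The resulting 7/24 lies close to the DFS of about 30% that section 3.2 gives without a time point.

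- True PFS after all 17 events: 7/24 = 29.2%, exact 95% interval 12.6% to 51.1%.
- When the event in position *j* is a censored death, its Kaplan-Meier factor (24−*j*)/(25−*j*) is dropped. The reading is therefore (7/24) × the product of (25−*j*)/(24−*j*) over the *k* deaths.
- Example, *k* = 1: first in order gives 7/23 = 30.4%; last in order gives 8/24 = 33.3%.

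| *k* | Lowest | Mean | Highest | Mean minus 29.2% |
|---|---|---|---|---|
| 0 | 29.2% | 29.2% | 29.2% | 0 |
| 1 | 30.4% | 31.4% | 33.3% | 2.2 points |
| 2 | 31.8% | 33.7% | 37.5% | 4.5 points |
| 3 | 33.3% | 36.3% | 41.7% | 7.1 points |

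**4. Effect on the median.** The true curve reaches 12/24 = 0.5 at the 12th event. The Kaplan-Meier median stays there only if every censored death falls among events 13 to 17; otherwise it moves later.

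- *k* = 1: unmoved in 5 of 17 orderings, later in 12 (71%), by one event.
- *k* = 2: unmoved in C(5,2) = 10 of 136, later in 126 (93%), by one or two events.
- *k* = 3: unmoved in C(5,3) = 10 of 680, later in 670 (99%), by one to three events.

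**5. The same effect in months.** With constant independent hazards, PFS median = time-to-progression median × (1 − share of first events that are deaths without progression). For an assumed time-to-progression median of 12 months:

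- share 5%: 12 × 0.95 = 11.4 months
- share 10%: 12 × 0.90 = 10.8 months
- share 20%: 12 × 0.80 = 9.6 months
- share 30%: 12 × 0.70 = 8.4 months

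**6. Censoring at the last scan instead.** Suppose one patient is censored at the last scan, 6 progressions follow, and then that patient dies. The reading is 17/23 = 73.9% throughout. The true value is 18/24 = 75.0% just before the death and 17/24 = 70.8% after it. The curve is slightly low before the death and too high afterwards.

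**The case against.** The best reply is that 6.2.2.12.3 is a short, unpolished paragraph and that no section says deaths are censored. It repeats its own starting point and gives OS no event at all, and 6.2.5.3.2 mentions death, so an analyst might count deaths by convention. That is possible, but the PFS sentence does name its end point and leaves death out, and the conventional reading is not written anywhere.

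The size is also open to challenge, and this part stands. The 17 events, *k*, the equal weighting of orderings and the absence of other censoring are all assumptions. Every reading in the table, at most 41.7%, lies inside the exact interval of 12.6% to 51.1%. PFS carries no test or threshold; the decision rests on response rate, and OS is reported separately.

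Two points about the remedy also stand. First, patients may go to surgery after cycle 4, and disease-status collection stops at new anti-cancer therapy. Adding death without a rule for these patients would count a late death after new therapy as an event, while a comparable living patient is censored at an earlier scan. Second, confirmed progression also appears in the discontinuation list in 5.8 and in the move to survival follow-up in 6.2.5.3.3, so editing that word in one place leaves the others out of step. Neither point alters the finding that death is missing from the definition.

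**Conclusion.** The definition is wrong as written and should be fixed. Read literally, it yields time to progression presented as PFS. When deaths without documented progression are censored, the curve after those deaths is generally too high and the median tends to be late. In the illustration the average excess is 2.2 to 7.1 percentage points for one to three such deaths; it is zero if there are none. These sizes rest on assumed event counts, because the documents supply none, and they are small beside the sampling error of 24 patients. The direction is nevertheless systematic. The consequence is confined to a descriptive secondary endpoint; the primary analysis and its power do not change.

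**What to change.** Replace the definition in 6.2.2.12.3, and repeat it in 7.1, with text such as:

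> PFS is the time from first dose of pembrolizumab to first documented progression by RECIST 1.1 (section 6.2.2.12.1) or death from any cause, whichever is first. Patients alive without progression are censored at their last disease assessment.

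For this endpoint, either drop the word confirmed or state what confirms progression. Time to progression may remain as a supportive summary under that name.

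In the same edit, state how surgery and new anti-cancer therapy are handled in the PFS analysis. Reconcile the endpoint wording with 5.8 and 6.2.5.3.3, and with section 5.3, which uses immune-related criteria for progression at cycle 2. These are separate from the error itself.

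Adding death needs no new visits or data: deaths are already captured through follow-up (6.2.5.3.2), survival calls (6.2.5.3.3) and serious adverse event reporting (6.3.3.1), and survival is part of the monitoring committee report (9.2.1). The reported median PFS may be shorter. The 24 patients, the primary test and its power stay as they are.
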